**T14.1.9.3 Summary of Subjects in Each Analysis Set**

| Number of Subjects   | GSP 301 placebo
NS pH [REDACTED]
(N=xxx
n (%)) | GSP 301 placebo
NS pH [REDACTED]
(N=xxx
n (%)) | GSP 301
NS
(N=xxx)
n (%) | Overall
(N=xxx)
n (%) |
|--|---|---|-----------------------------------|-----------------------------|
| Randomized   | xxx (xx.x)  | xxx (xx.x)  | xxx (xx.x)                        | xxx (xx.x)                  |
| Safety analysis set  | xxx (xx.x)  | xxx (xx.x)  | xxx (xx.x)                        | xxx (xx.x)                  |
| Did not take any study medication                                      | xxx (xx.x)  | xxx (xx.x)  | xxx (xx.x)                        | xxx (xx.x)                  |
| Full analysis set  | xxx (xx.x)  | xxx (xx.x)  | xxx (xx.x)                        | xxx (xx.x)                  |
| Did not have at least one post-baseline
primary AM rTNSS assessment | xxx (xx.x)  | xxx (xx.x)  | xxx (xx.x)                        | xxx (xx.x)                  |
| Per protocol set   | xxx (xx.x)  | xxx (xx.x)  | xxx (xx.x)                        | xxx (xx.x)                  |
| Subjects with Major protocol violation                                 | xxx (xx.x)  | xxx (xx.x)  | xxx (xx.x)                        | xxx (xx.x)                  |
| RQLQ(S) Analysis Set   | xxx (xx.x)  | xxx (xx.x)  | xxx (xx.x)                        | xxx (xx.x)                  |

Data source: xx

Created on: ddmmyy hh:mm

Page 1 of N

|  |                                    |                                  |
|--|------------------------------------|----------------------------------|
| Protocol Number:
GPL/CT/2014/018/III
(Study No. GSP 301-303) | SAP Version Number:
Version 1.0 | SAP Version Date:
04-Apr-2017 |
|--|------------------------------------|----------------------------------|

**T14.1.9.4.1 Summary of Demographic Data  
(Safety Analysis Set)**

|                 |   | GSP 301 placebo
NS pH [REDACTED]
(N=xxx) | GSP 301 placebo
NS pH [REDACTED]
(N=xxx) | GSP 301
NS
(N=xxx) | Overall
(N=xxx) |
|-----------------|---|--|--|--------------------------|--------------------|
| Age             | n   | xxx  | xxx  | xxx                      | xxx                |
|                 | Mean (SD)                                 | xx.x (xx.x)                                    | xx.x (xx.x)                                    | xx.x (xx.x)              | xx.x (xx.x)        |
|                 | Median                                    | xx.x   | xx.x   | xx.x                     | xx.x               |
|                 | Min, Max                                  | xx.x, xx.x                                     | xx.x, xx.x                                     | xx.x, xx.x               | xx.x, xx.x         |
|                 | Race n (%)                                |  |  |                          |                    |
|                 | White                                     | xxx (xx.x)                                     | xxx (xx.x)                                     | xxx (xx.x)               | xxx (xx.x)         |
|                 | Asian                                     | xxx (xx.x)                                     | xxx (xx.x)                                     | xxx (xx.x)               | xxx (xx.x)         |
|                 | American Indian or Alaska Native          | xxx (xx.x)                                     | xxx (xx.x)                                     | xxx (xx.x)               | xxx (xx.x)         |
|                 | Black/African American                    | xxx (xx.x)                                     | xxx (xx.x)                                     | xxx (xx.x)               | xxx (xx.x)         |
|                 | Native Hawaiian or other Pacific Islander | xxx (xx.x)                                     | xxx (xx.x)                                     | xxx (xx.x)               | xxx (xx.x)         |
|                 | Other                                     | xxx (xx.x)                                     | xxx (xx.x)                                     | xxx (xx.x)               | xxx (xx.x)         |
| Ethnicity n (%) | Hispanic or Latino                        | xxx (xx.x)                                     | xxx (xx.x)                                     | xxx (xx.x)               | xxx (xx.x)         |
|                 | Not Hispanic or Latino                    | xxx (xx.x)                                     | xxx (xx.x)                                     | xxx (xx.x)               | xxx (xx.x)         |
| Sex n (%)       | Male                                      | xxx (xx.x)                                     | xxx (xx.x)                                     | xxx (xx.x)               | xxx (xx.x)         |
|                 | Female                                    | xxx (xx.x)                                     | xxx (xx.x)                                     | xxx (xx.x)               | xxx (xx.x)         |

N= number of subjects in the treatment group; n= number of subjects with data available; % is based on N in the treatment group

Data source: xx

Created on: ddmmmyy hh:mm

Page 1 of N

|  |                                    |                                  |
|--|------------------------------------|----------------------------------|
| Protocol Number:
GPL/CT/2014/018/III
(Study No. GSP 301-303) | SAP Version Number:
Version 1.0 | SAP Version Date:
04-Apr-2017 |
|--|------------------------------------|----------------------------------|

**T14.1.9.4.2 Summary of Demographic Data  
(Full Analysis Set)**

Repeat of T14.1.9.4.1 for FAS

**T14.1.9.4.3 Summary of Demographic Data  
(Per Protocol Set)**

Repeat of T14.1.9.4.1 for PPS

**T14.1.9.4.4 Summary of Demographic Data  
(RQLQ(S) Analysis Set)**

Repeat of T14.1.9.4.1 for RQLQ(S) analysis set

|  |                                    |                                  |
|--|------------------------------------|----------------------------------|
| Protocol Number:
GPL/CT/2014/018/III
(Study No. GSP 301-303) | SAP Version Number:
Version 1.0 | SAP Version Date:
04-Apr-2017 |
|--|------------------------------------|----------------------------------|

**T14.1.9.5.1 Overall Summary of Treatment Emergent Adverse Events after 52 Weeks of Study Treatment  
(Safety Analysis Set)**

|   | GSP 301 placebo
NS pH [REDACTED]
(N=xxx) | GSP 301 placebo
NS pH [REDACTED]
(N=xxx) | GSP 301
NS
(N=xxx) |
|---|--|--|--------------------------|
| Subjects in Safety Analysis Set (N1)            | xxx  | xxx  | xxx                      |
| Subjects with at least one TEAE (n1(%))         | xxx (xx.x)                                     | xxx (xx.x)                                     | xxx (xx.x)               |
| Discontinued study drug due to above AE (n1(%)) | xxx (xx.x)                                     | xxx (xx.x)                                     | xxx (xx.x)               |
| TEAEs reported (N2)                             | xxx  | xxx  | xxx                      |
| Mild (n2(%))                                    | xxx (xx.x)                                     | xxx (xx.x)                                     | xxx (xx.x)               |
| Moderate (n2(%))                                | xxx (xx.x)                                     | xxx (xx.x)                                     | xxx (xx.x)               |
| Severe (n2(%))                                  | xxx (xx.x)                                     | xxx (xx.x)                                     | xxx (xx.x)               |
| Not Related (n2(%))                             | xxx (xx.x)                                     | xxx (xx.x)                                     | xxx (xx.x)               |
| Related (n2(%))                                 | xxx (xx.x)                                     | xxx (xx.x)                                     | xxx (xx.x)               |
| Death (n2(%))                                   | xxx (xx.x)                                     | xxx (xx.x)                                     | xxx (xx.x)               |
| Serious AE (n2(%))                              | xxx (xx.x)                                     | xxx (xx.x)                                     | xxx (xx.x)               |

N1: number of subjects in safety analysis sets in treatment group; n1(%): percentage based on N1

N2: number of adverse events in treatment group; n2(%): percentage based on N2

Data source: xx

Created on: ddmmmyy hh:mm

Page 1 of N

**T14.1.9.5.2 Overall Summary of Treatment Emergent Adverse Events after 30 Weeks of Study Treatment  
(Safety Analysis Set)**

Repeat of T14.1.9.5.1 for after 30 weeks of study treatment

|  |                                    |                                  |
|--|------------------------------------|----------------------------------|
| Protocol Number:
GPL/CT/2014/018/III
(Study No. GSP 301-303) | SAP Version Number:
Version 1.0 | SAP Version Date:
04-Apr-2017 |
|--|------------------------------------|----------------------------------|

**T14.1.9.5.3 Summary of Treatment Emergent Adverse Events after 52 Weeks of Study Treatment  
(Safety Analysis Set)**

| Body System                    | MedDRA Term | GSP 301 placebo
NS pH [REDACTED]
(N=xxx) |                  | GSP 301 placebo
NS pH [REDACTED]
(N=xxx) |                  | GSP 301
NS
(N=xxx) |                  | Fisher's
P-value |
|--------------------------------|-------------|--|------------------|--|------------------|--------------------------|------------------|---------------------|
|                                |             | Events   | Subjects
n(%) | Events   | Subjects
n(%) | Events                   | Subjects
n(%) |                     |
| Subjects with at least one AEs | Total       | xxx  | xxx (xx.x)       | xxx  | xxx (xx.x)       | xxx                      | xxx (xx.x)       | x.xxxx              |
| Ear and labyrinth disorders    | Ear pain    | xxx  | xxx (xx.x)       | xxx  | xxx (xx.x)       | xxx                      | xxx (xx.x)       | x.xxxx              |
|                                | etc.        |  |                  |  |                  |                          |                  |                     |

etc.

N = Total number of subjects in each treatment group in the safety set; n = number of subjects with adverse events in each MedDRA term; Percentages are based on total number of subjects in the safety set within each treatment group.

Data source: xx

Created on: ddmmmyy hh:mm

Page 1 of N

|  |                                    |                                  |
|--|------------------------------------|----------------------------------|
| Protocol Number:
GPL/CT/2014/018/III
(Study No. GSP 301-303) | SAP Version Number:
Version 1.0 | SAP Version Date:
04-Apr-2017 |
|--|------------------------------------|----------------------------------|

**T14.1.9.5.4 Summary of Treatment Emergent Adverse Events after 30 Weeks of Study Treatment  
(Safety Analysis Set)**

Repeat of T14.1.9.5.3 for after 30 weeks of study treatment

**T14.1.9.5.5 Summary of Treatment-Related Emergent Adverse Events after 52 Weeks of Study Treatment  
(Safety Analysis Set)**

Repeat of T14.1.9.5.3 for related TEAEs after 52 weeks of study treatment

**T14.1.9.5.6 Summary of Treatment-Related Emergent Adverse Events after 30 Weeks of Study Treatment  
(Safety Analysis Set)**

Repeat of T14.1.9.5.3 for related TEAEs after 30 weeks of study treatment

**T14.1.9.5.7 Summary of Treatment Emergent Adverse Events of Special Interest  
(Safety Analysis Set)**

Repeat of T14.1.9.5.3 for AESI

**T14.1.9.5.8 Summary of Treatment Related Emergent Adverse Events of Special Interest  
(Safety Analysis Set)**

Repeat of T14.1.9.5.3 for related TEAEs of AESI

|  |                                    |                                  |
|--|------------------------------------|----------------------------------|
| Protocol Number:
GPL/CT/2014/018/III
(Study No. GSP 301-303) | SAP Version Number:
Version 1.0 | SAP Version Date:
04-Apr-2017 |
|--|------------------------------------|----------------------------------|

**T14.1.9.5.9 Summary of Treatment Emergent Adverse Events after 52 Weeks of Study Treatment by Severity  
(Safety Analysis Set)**

| Body System                       | MedDRA Term | GSP 301 placebo
NS pH [REDACTED]
# of Events
(N=xx) |                  |                | GSP 301 placebo
NS pH [REDACTED]
# of Events
(N=xx) |                  |                | GSP 301
NS
# of Events
(N=xx) |                  |                |
|-----------------------------------|-------------|--|------------------|----------------|--|------------------|----------------|--|------------------|----------------|
|                                   |             | Mild
n(%)   | Moderate
n(%) | Severe
n(%) | Mild
n(%)   | Moderate
n(%) | Severe
n(%) | Mild
n(%)                           | Moderate
n(%) | Severe
n(%) |
| Total AEs                         | Total       | xx (xx.x)  | xx (xx.x)        | xx (xx.x)      | xx (xx.x)  | xx (xx.x)        | xx (xx.x)      | xx (xx.x)                              | xx (xx.x)        | xx (xx.x)      |
| Ear and
labyrinth
disorders | Ear pain    | xx (xx.x)  | xx (xx.x)        | xx (xx.x)      | xx (xx.x)  | xx (xx.x)        | xx (xx.x)      | xx (xx.x)                              | xx (xx.x)        | xx (xx.x)      |

N = Total number of subjects in each treatment group in the safety set; n = number of subjects with adverse events in each MedDRA term;  
Percentages are based on total number of subjects in the safety set within each treatment group

Data source: xx

Created on: ddmmmyy hh:mm

Page 1 of N

|  |                                    |                                  |
|--|------------------------------------|----------------------------------|
| Protocol Number:
GPL/CT/2014/018/III
(Study No. GSP 301-303) | SAP Version Number:
Version 1.0 | SAP Version Date:
04-Apr-2017 |
|--|------------------------------------|----------------------------------|

**T14.1.9.5.10 Summary of Treatment Emergent Adverse Events after 30 Weeks of Study Treatment by Severity  
(Safety Analysis Set)**

Repeat of T14.1.9.5.9 for after 30 weeks of study treatment

**T14.1.9.5.11 Summary of Treatment Emergent Adverse Events of Special Interest by Severity  
(Safety Analysis Set)**

Repeat of T14.1.9.5.9 for AESI

|  |                                    |                                  |
|--|------------------------------------|----------------------------------|
| Protocol Number:
GPL/CT/2014/018/III
(Study No. GSP 301-303) | SAP Version Number:
Version 1.0 | SAP Version Date:
04-Apr-2017 |
|--|------------------------------------|----------------------------------|

**T14.1.9.5.12 Summary of Treatment Emergent Adverse Events after 52 Weeks of Study Treatment by Relationship to Study Treatment (Safety Analysis Set)**

| Body System                       | MedDRA Term | GSP 301 placebo
NS pH [REDACTED]
# of Events
(N=xx) |                     | GSP 301 placebo
NS pH [REDACTED]
# of Events
(N=xx) |                     | GSP 301
NS
# of Events
(N=xx) |                     |
|-----------------------------------|-------------|--|---------------------|--|---------------------|--|---------------------|
|                                   |             | Related
n(%)  | Not Related
n(%) | Related
n(%)  | Not Related
n(%) | Related
n(%)                        | Not Related
n(%) |
| Total AEs                         | Total       | xx (xx.x)  | xx (xx.x)           | xx (xx.x)  | xx (xx.x)           | xx (xx.x)                              | xx (xx.x)           |
| Ear and
labyrinth
disorders | Ear pain    | xx (xx.x)  | xx (xx.x)           | xx (xx.x)  | xx (xx.x)           | xx (xx.x)                              | xx (xx.x)           |

N = Total number of subjects in each treatment group in the safety set; n = number of subjects with adverse events in each MedDRA term;  
Percentages are based on total number of subjects in the safety set within each treatment group

Data source: xx

Created on: ddmmmyy hh:mm

Page 1 of N

|  |                                    |                                  |
|--|------------------------------------|----------------------------------|
| Protocol Number:
GPL/CT/2014/018/III
(Study No. GSP 301-303) | SAP Version Number:
Version 1.0 | SAP Version Date:
04-Apr-2017 |
|--|------------------------------------|----------------------------------|

**T14.1.9.5.13 Summary of Treatment Emergent Adverse Events after 30 Weeks of Study Treatment by Relationship to Study Treatment  
(Safety Analysis Set)**

Repeat of T14.1.9.5.12 for after 30 weeks of study treatment

**T14.1.9.5.14 Summary of Treatment Emergent Adverse Events of Special Interest by Relationship to Study Treatment  
(Safety Analysis Set)**

Repeat of T14.1.9.5.12 for AESI

|  |                                    |                                  |
|--|------------------------------------|----------------------------------|
| Protocol Number:
GPL/CT/2014/018/III
(Study No. GSP 301-303) | SAP Version Number:
Version 1.0 | SAP Version Date:
04-Apr-2017 |
|--|------------------------------------|----------------------------------|

**T14.1.9.5.15 Summary of Treatment Emergent Serious Adverse Events after 52 Weeks of Study Treatment  
(Safety Analysis Set)**

| Body System                   | MedDRA Term                   | GSP 301 placebo
NS pH [REDACTED]
(N=xxx)
n(%) | GSP 301 placebo
NS pH [REDACTED]
(N=xxx)
n(%) | GSP 301
NS
(N=xxx)
n(%) |
|-------------------------------|-------------------------------|--|--|----------------------------------|
| Subject with at least one SAE | Subject with at least one SAE | xxx (xx.x)   | xxx(xx.x)  | xxx(xx.x)                        |
| Gastrointestinal disorders    | Dry mouth                     | xxx (xx.x)   | xxx (xx.x)   | xxx(xx.x)                        |
| etc.                          | etc.                          |  |  |                                  |

N = Total number of subjects in each treatment group in the safety set;  
n = number of subjects with adverse events in each MedDRA term;  
Percentages are based on total number of subjects in the safety set within each treatment group

Data source: xx

Created on: ddmmmyy hh:mm

Page 1 of N

|  |                                    |                                  |
|--|------------------------------------|----------------------------------|
| Protocol Number:
GPL/CT/2014/018/III
(Study No. GSP 301-303) | SAP Version Number:
Version 1.0 | SAP Version Date:
04-Apr-2017 |
|--|------------------------------------|----------------------------------|

**T14.1.9.5.16 Summary of Treatment Emergent Serious Adverse Events after 30 Weeks of Study Treatment  
(Safety Analysis Set)**

Repeat of T14.1.9.5.15 for after 30 weeks of study treatment

**T14.1.9.5.17 Summary of Treatment Related Emergent Serious Adverse Events after 52 Weeks of Study Treatment  
(Safety Analysis Set)**

Repeat of T14.1.9.5.15 for treatment emergent SAE after 52 weeks of study treatment

**T14.1.9.5.18 Summary of Treatment Related Emergent Serious Adverse Events after 30 Weeks of Study Treatment  
(Safety Analysis Set)**

Repeat of T14.1.9.5.15 for treatment emergent SAE after 30 weeks of study treatment

|  |                                    |                                  |
|--|------------------------------------|----------------------------------|
| Protocol Number:
GPL/CT/2014/018/III
(Study No. GSP 301-303) | SAP Version Number:
Version 1.0 | SAP Version Date:
04-Apr-2017 |
|--|------------------------------------|----------------------------------|

**T14.1.9.5.19.1 Overall Summary of Adverse Events During Placebo Run-In Period  
(Safety Analysis Set)**

|   | GSP 301 placebo
NS pH [REDACTED] | GSP 301 placebo
NS pH [REDACTED] | GSP 301
NS |
|---|-------------------------------------|-------------------------------------|---------------|
| Subjects in Safety Analysis Set (N1)          | xxx                                 | xxx                                 | xxx           |
| Subjects with at least one AE n1(%)           | xxx (xx.x)                          | xxx (xx.x)                          | xxx (xx.x)    |
| Discontinued study drug due to above AE n1(%) | xxx (xx.x)                          | xxx (xx.x)                          | xxx (xx.x)    |
| AEs reported (N2)                             | xxx                                 | xxx                                 | xxx           |
| Mild n2(%)                                    | xxx (xx.x)                          | xxx (xx.x)                          | xxx (xx.x)    |
| Moderate n2(%)                                | xxx (xx.x)                          | xxx (xx.x)                          | xxx (xx.x)    |
| Severe n2(%)                                  | xxx (xx.x)                          | xxx (xx.x)                          | xxx (xx.x)    |
| Not Related n2(%)                             | xxx (xx.x)                          | xxx (xx.x)                          | xxx (xx.x)    |
| Related n2(%)                                 | xxx (xx.x)                          | xxx (xx.x)                          | xxx (xx.x)    |
| Death n2(%)                                   | xxx (xx.x)                          | xxx (xx.x)                          | xxx (xx.x)    |
| Serious AE n2(%)                              | xxx (xx.x)                          | xxx (xx.x)                          | xxx (xx.x)    |

N1: number of subjects in safety analysis sets in treatment group; n1(%): percentage based on N1

N2: number of adverse events in treatment group; n2(%): percentage based on N2

Data source: xx

Created on: ddmmmyy hh:mm

Page 1 of N

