13.7.2 Adverse Events

Adverse events will be coded using the current Medical Dictionary for Regulatory Activities (MedDRA). Adverse events occurring between the signing of informed consent and administration of the first dose of randomized study medication will be regarded as pre-treatment AEs and included in the subject listings but not in the summary tables. Adverse events occurring after the first dose of randomized study medication will be defined as TEAEs.

The safety endpoints related to AEs are:

- Proportion of subjects with TEAEs.
- Proportion of subjects with treatment-related TEAEs.
- Incidence, type, and severity of the TEAEs after 30 weeks of study treatment.
- Incidence, type, and severity of the TEAEs after 52 weeks of study treatment.

The number and percentage of subjects with TEAEs will be summarized by study treatment group, overall, and by system organ class (SOC) and preferred term (PT) using frequency counts and percentages. The summaries will also include the number of TEAEs experienced. A similar summary will be produced for subjects with treatment-related TEAE.

The number and percentage of subjects with a TEAE that has a start date within 30 weeks of the start of treatment (≤ 182 days) will be summarized by severity and study treatment group, overall, and by SOC and PT using frequency counts and percentages. A similar summary will be produced including all TEAEs during the study (i.e., after 52 weeks of treatment).

If sufficient data exist, TEAE frequencies will be compared across treatment groups using Fisher's exact test or a similar test.

Additionally, the number and percentage of SAEs, TEAEs leading to discontinuation, and TEAEs related to the IP will be summarized by SOC, PT, and study treatment group. All AEs will be displayed in listings. AEs that occur during the run-in period will be summarized separately.

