### **Safety Analysis Set (SAS)**

The Safety Analysis Set (SAS) will consist of all subjects who took at least 1 dose of study medication following randomization and will be used for all safety analyses.

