**Table 2: Overview of Planned Safety Analyses**

| Display Type                    | Data Displays Generated |        |         |
|---------------------------------|-------------------------|--------|---------|
|                                 | Table                   | Figure | Listing |
| Adverse Events           |                         |        |         |
| Overview                        | Y[2]                    |        |         |
| Treatment Emergent AEs          | Y[1][2]                 |        | Y       |
| Treatment Emergent AEs Severity | Y[2]                    |        | Y       |
| Drug-Related AEs                | Y[2]                    |        | Y       |
| Placebo Run-In Period AEs       | Y[2]                    |        | Y       |
| AEs Leading to Withdrawal       |                         |        | Y       |
| SAEs                            | Y[2]                    |        | Y       |
| Treatment Emergent SAEs         | Y[2]                    |        | Y       |
| Laboratory               |                         |        |         |
| Biochemistry                    | Y[3] [2]                |        | Y       |
| Haematology                     | Y[3] [2]                |        | Y       |
| Urinalysis                      | Y[3] [2]                |        | Y       |
| Pregnancy Test Results          |                         |        | Y       |
| Other                    |                         |        |         |
| Vital Signs                     | Y[4] [2]                |        | Y       |
| ECGs                            | Y [5] [2]               |        | Y       |
| Physical Examination            | Y[6] [2]                |        | Y       |
| Focused ENT Examination         | Y[7] [2]                |        | Y       |

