**NOTES :**

- Y = Yes display generated.
- [1]: Display will also be produced by SOC, severity, and by relationship to study medication
- [2]: Display will be based on safety analysis set
- [3]: Display will be produced separately for overall laboratory assessments (inc. change from baseline), change from baseline in laboratory results, and potentially clinically significant laboratory results, and shift tables
- [4]: Display will be produced separately for overall summary (inc. change from baseline), for potentially clinically significant results, and shift tables
- [5]: Display will be produced separately for overall summary (inc. change from baseline), change from baseline in ECG interpretation, and potentially clinical significant ECGs, and shift tables
- [6]: Display will be produced separately for overall summary, and for potentially clinically significant results
- [7]: Display will be produced separately for overall summary, and for

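### The run-in adverse event table covers only subjects later randomized and dosed, so exits and deaths during the run-in cannot appear in it

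*SAP*

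**What the plan says.** Protocol Section 13.7.2 states that "AEs that occur during the run-in period will be summarized separately", with no restriction to subjects who are later randomized. Earlier in the same section it also says that events between consent and the first randomized dose go into listings and not into summary tables. SAP Section 12.2.2 repeats that second statement.

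The SAP then plans two summary tables of such events in Appendix 1. The first, T14.1.9.5.19.1, "Overall Summary of Adverse Events During Placebo Run-In Period", carries the Safety Analysis Set in its title. It has one column for each of the three randomized arms and no total. It includes rows for stopping study drug because of the event and for death. Its footnote reads "N1: number of subjects in safety analysis sets in treatment group; n1(%): percentage based on N1". In SAP Table 2 the row "Placebo Run-In Period AEs" carries note [2], which names the safety analysis set as the basis. SAP Section 10.0 says that this set "will consist of all subjects who took at least 1 dose of study medication following randomization", and Protocol Section 13.2 gives the same definition.

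The second table, T14.1.9.5.19.2, has no analysis set in its title and is specified only as a repeat of the first shell for the pre-randomization period. Listing L16.2.7.2 (run-in adverse events) also carries no analysis set. The disposition table T14.1.9.1 counts subjects treated in the run-in and subjects who failed randomization, as single totals without reasons.

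**The concern.** Every subject takes the same single-blind placebo spray in the run-in. A summary of run-in events should therefore describe everyone who used that spray. As specified, it describes only those who got through the run-in, were randomized and took a randomized dose.

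The exclusion depends on the outcome being tabulated. Under Protocol Section 9.3, criterion 2 bars randomization after an event that breaks the inclusion criteria. Criterion 7 bars it after a cold, respiratory infection, otitis media or acute sinusitis in the preceding 14 days. Exclusion criterion 15 also covers respiratory infections that develop during the run-in. People with events are removed, and the event rate is then computed on those who remain.

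At stake is a descriptive result. A reader of the report would see no one leaving the run-in because of an event, and could take that as a finding about the vehicle when it follows from the choice of population. Protocol Section 5.5 treats vehicle pH as an issue for interpreting the safety data, so the reader has reason to look at this table.

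**Working it through.** The plan states no figure to reproduce, so the check is one of set membership, followed by the direction of the bias.

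**Membership**
1. Population of T14.1.9.5.19.1 = Safety Analysis Set (table title, N1 row and footnote; SAP Table 2, note [2]).
2. Safety Analysis Set = at least one dose after randomization (SAP Section 10.0; Protocol Section 13.2).
3. A subject who leaves during the run-in because of an event has no dose after randomization, and so is outside the set.
4. Protocol Section 11.1 bars re-screening of anyone who enters the run-in and then fails the randomization criteria, so the subject cannot join the set later. A narrow opening remains: Protocol Section 11 and Appendix 1, note b, mention re-screening when an ENT referral causes delay.
5. Leaving that opening aside, run-in exits due to an event, and run-in deaths, number 0 in every column whatever happened.

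**What can still appear**
- The discontinuation or death row can be non-zero if an event that began in the run-in later stops double-blind drug or proves fatal after randomization.
- A subject who only skipped some run-in doses can still meet the 80% dosing rule of criterion 6 (6/7 = 86%; 8/10 = 80%), be randomized and be counted.

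**Direction of the bias in the event rate**
Let n_R be the run-in subjects who enter the safety set and n_F those who do not, with proportions p_R and p_F having at least one run-in event. Let f = n_F/(n_R + n_F).
- Printed rate = p_R.
- Rate in everyone treated = (n_R·p_R + n_F·p_F)/(n_R + n_F) = p_R + f·(p_F − p_R).
- Printed minus full = −f·(p_F − p_R).

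The printed rate is too low whenever p_F exceeds p_R. Criteria 2 and 7 make that the expected case, because they place subjects in the excluded group for having an event. Criteria 3 to 6 (symptom score, congestion score, diary and dosing compliance) can be failed with no event at all, which dilutes p_F. The documents give neither f nor p_F, so no number can be attached.

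**Do the other outputs fill the gap?**

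| Output | Set named | Place for unrandomized subjects |
|---|---|---|
| T14.1.9.5.19.1 | Safety Analysis Set | None |
| T14.1.9.5.19.2 | None | None in the repeated shell; intent unstated |
| L16.2.7.2 | None | Possible (listing) |
| T14.1.9.1 | None | Total count only, no reasons |

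No summary with a stated population counts these subjects' events.

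**The case against.** The SAP can be read as following its instructions. Protocol Section 13.2 assigns the Safety Analysis Set to all safety analyses, and both documents say that pre-treatment events stay out of summary tables. The sibling outputs T14.1.9.5.19.2 and L16.2.7.2 drop the label carried by their neighbours, perhaps deliberately, to take in unrandomized subjects. SAP Appendix 1 says that shells are a framework and that headers and footnotes will be changed as needed. A by-arm view of run-in events in the safety population is also a legitimate description.

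Much of this stands. The conflict begins in the protocol, the population of T14.1.9.5.19.2 is unstated rather than wrong, and the by-arm columns need not go. None of it gives T14.1.9.5.19.1 a population that fits an unrestricted run-in summary.

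A reader might infer three stronger things that the documents do not support.
- **That the primary safety comparison is biased.** It is not. The primary adverse event endpoints are events after the first randomized dose, and run-in losses occur before randomization.
- **That this table is the only evidence, or the largest sample, on vehicle tolerability.** L16.2.7.2 may list the missing events, with relationship and action taken. The run-in is largest only by headcount. For the 600 randomized subjects it gives 600 × 7 = 4,200 to 600 × 10 = 6,000 subject-days. One placebo arm of 100 gives about 100 × 364 × 0.75 = 27,300, if the attrition assumed for sample size (25% by 6 months, 50% by 52 weeks) applies to placebo and losses are linear.
- **That hundreds of subjects' events are hidden.** A run-in failure share of 20% to 40% would mean 600/0.80 − 600 = 150 to 600/0.60 − 600 = 400 absent subjects. That share is an assumption with no source in the documents, and it counts people, not events.

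**Conclusion.** The point holds, as a minor one. T14.1.9.5.19.1 excludes by rule every subject who left the run-in because of an event and never received a randomized dose. Run-in exits and run-in deaths are therefore zero by construction, and the overall run-in event rate is expected to be low by an unknown amount. The zero follows from the definitions alone. The downward direction assumes that subjects who did not reach the safety set had run-in events more often than those who did, which criteria 2 and 7 make likely but do not prove. No primary or secondary endpoint changes. It would go too far to say that the events are unreported, since L16.2.7.2 is not limited to the safety set.

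**What to change.** - **T14.1.9.5.19.1:** use all subjects who took at least one dose of run-in placebo, with a total column. A split into randomized and not randomized is optional, and the by-arm columns may stay. Amend the title, the N1 row, the footnote, and note [2] for that row of SAP Table 2.
- **T14.1.9.5.19.2:** state that it covers all consented subjects with a pre-randomization event, including those never randomized, and give it a total column. Do not limit it to subjects dosed in the run-in. Protocol Section 12.4.5 collects events from consent, and such a limit would drop events in subjects never dosed.
- **T14.1.9.1:** add the reason for not being randomized (adverse event or other).
- **Protocol Section 13.7.2 and SAP Section 12.2.2:** reconcile the statement that pre-treatment events are not in summary tables with these two planned tables. SAP Section 1.0, which records changes from the protocol, is a natural place, and it can also note the exception to using the safety set for all safety analyses.

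The cost is a change to SAP text and shells plus modest programming. The events are already collected. The one item to confirm is that the case report form records why a run-in subject was not randomized; Protocol Section 7.1 describes a Screening Disposition page with reasons for screen failure.
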